#### **6.1.3.4 Infusion Visits 2, 3, 4, 5, and 6 (Weeks 3, 5, 7, 9, and 11 $\pm$ 3 Days, respectively)**

The following procedures and assessments will be performed prior to administration of IMP:

- Enter the IWRS and register subject visit data.
- Alcohol TLFB (This will be given to the subject at the beginning of the visit and will be considered source documentation.) (Infusion Visit 5)
- Assessment of cirrhosis complications (Infusion Visits 3 and 5).
- Perform a limited physical examination (including weight and examination of the heart, lung, and abdomen).

- Collect vital sign measurements (including heart and respiratory rate, blood pressure, and body temperature).
- Perform urine pregnancy test (females of childbearing potential only) (Infusion Visits 3 and 5).

The following information will be collected after IMP administration:

- AE monitoring.
- Record concomitant medications.

The following will be performed 2 hours after the end of the IMP infusion

- Collect PK sample (Infusion Visits 2, 3, and 4)

#### **6.1.3.5 Infusion Visit 7 (Week 13 ± 3 Days)**

The following procedures and assessments will be performed prior to administration of IMP:

- Enter the IWRS and register subject visit data
- Assessment of cirrhosis complications
- Perform a limited physical examination (including weight and examination of the heart, lung, and abdomen)
- Collect vital sign measurements (including heart and respiratory rate, blood pressure, and body temperature)
- Perform urine pregnancy test (females of childbearing potential only)
- Perform hematology testing
- Perform blood chemistry testing

The following information will be collected after IMP administration:

- AE monitoring

- Record concomitant medications

The following will be performed 2 hours after the end of the IMP infusion

- Collect PK sample

### **6.1.3.6 Infusion Visits 8, 9, 10, 11, and 12 (Weeks 15, 17, 19, 21, and 23 ± 3 Days)**

The following procedures and assessments will be performed prior to administration of IMP:

- Enter the IWRS and register subject visit data.
- Assessment of cirrhosis complications (Infusion Visits 9 and 11).
- Alcohol TLFB (This will be given to the subject at the beginning of the visit and will be considered source documentation.) (Infusion Visit 9)
- Perform a limited physical examination including weight and examination of the heart, lung, and abdomen).
- Collect vital sign measurements (including heart and respiratory rate, blood pressure, and body temperature).
- Perform urine pregnancy test (females of childbearing potential only) (Infusion Visits 9 and 11).

The following information will be collected after IMP administration:

- AE monitoring.
- Record concomitant medications.

The following will be collected 2 hours after IMP infusion

- Collect PK sample (Infusion Visit 10).

### **6.1.3.7 Infusion Visit 13 (Week 25 ± 3 Days)**

The following procedures and assessments will be performed prior to administration of IMP:

- Enter the IWRS and register subject visit data.
- Alcohol TLFB (This questionnaire will be given to the subject at the beginning of the visit and will be considered source documentation.)
- Assessment of cirrhosis complications.
- Perform a limited physical examination (including weight and examination of the heart, lung, and abdomen).
- Collect vital sign measurements (including heart and respiratory rate, blood pressure, and body temperature).
- Perform urine pregnancy test (females of childbearing potential only).
- Perform hematology testing.
- Perform blood chemistry testing.
- Obtain MELD score.
- Conduct a FibroScan.
- Perform MBT (if available).
- Collect biomarkers blood sample (will include the ELF test, FibroTest [FibroSure], and galectin-3).
- Collect plasma and serum sample for storage at  $-20^{\circ}\text{C}$ .

The following information will be collected after IMP administration:

- Perform a 12-lead ECG assessment.
- Obtain Child-Turcotte-Pugh score and class (A, B, or C).
- AE monitoring.
- Record concomitant medications.

The following will be collected 2 hours after the end of the IMP infusion

- Collect PK sample

#### **6.1.3.8 Infusion Visits 14, 15, 16, 17, 18, and 19 (Weeks 27, 29, 31, 33, 35, and 37 ± 3 Days)**

The following procedures and assessments will be performed prior to administration of IMP:

- Enter the IWRS and register subject visit data.
- Alcohol TLFB (This questionnaire will be given to the subject at the beginning of the visit and will be considered source documentation.) (Infusion Visit 17)
- Assessment of cirrhosis complications (Infusion Visits 15, 17, and 19).
- Perform a limited physical examination (including weight and examination of the heart, lung, and abdomen).
- Collect vital sign measurements (including heart and respiratory rate, blood pressure, and body temperature).
- Perform urine pregnancy test (females of childbearing potential only) (Infusion Visits 15, 17, and 19).

The following information will be collected after IMP administration:

- AE monitoring.
- Record concomitant medications.

#### **6.1.3.9 Infusion Visit 20 (Week 39 ± 3 Days)**

The following procedures and assessments will be performed prior to administration of IMP:

- Enter the IWRS and register subject visit data
- Perform a limited physical examination (including weight and examination of the heart, lung, and abdomen)

- Collect vital sign measurements (including heart and respiratory rate, blood pressure, and body temperature)
- Perform hematology testing
- Perform blood chemistry testing

The following information will be collected after IMP administration:

- AE monitoring
- Record concomitant medications

#### **6.1.3.10 Infusion Visit 21 (Week 41 ± 3 Days)**

The following procedures and assessments will be performed prior to administration of IMP:

- Enter the IWRS and register subject visit data.
- Alcohol TLFB (This questionnaire will be given to the subject at the beginning of the visit and will be considered source documentation.)
- Assessment of cirrhosis complications.
- Perform a limited physical examination (including weight and examination of the heart, lung, and abdomen).
- Collect vital sign measurements (including heart and respiratory rate, blood pressure, and body temperature).
- Perform urine pregnancy test (females of childbearing potential only).

The following information will be collected after IMP administration:

- AE monitoring.
- Record concomitant medications.

### **6.1.3.11 Infusion Visits 22, 23, 24, and 25 (Weeks 43, 45, 47, and 49 ± 3 Days)**

The following procedures and assessments will be performed prior to administration of IMP:

- Enter the IWRS and register subject visit data.
- Alcohol TLFB (This questionnaire will be given to the subject at the beginning of the visit and will be considered source documentation.) (Infusion Visit 25)
- Assessment of cirrhosis complications (Infusion Visits 23 and 25).
- Perform a limited physical examination including weight and examination of the heart, lung, and abdomen).
- Collect vital sign measurements (including heart and respiratory rate, blood pressure, and body temperature).
- Perform urine pregnancy test (females of childbearing potential only) (Infusion Visits 23 and 25).

The following information will be collected after IMP administration:

- AE monitoring.
- Record concomitant medications.

### **6.1.3.12 Infusion Visit 26 (Week 51 ± 3 Days)**

The following procedures and assessments will be performed prior to administration of IMP:

- Enter the IWRS and register subject visit data.
- CLDQ (This questionnaire will be given to the subject at the beginning of the visit and will be considered source documentation.)
- Assessment of cirrhosis complications.

- Perform a limited physical examination (including weight and examination of the heart, lung, and abdomen).
- Collect vital sign measurements (including heart and respiratory rate, blood pressure, and body temperature).
- Perform hematology testing.
- Perform blood chemistry testing.
- Obtain MELD score.
- Collect plasma and serum sample for freezing at  $-20^{\circ}\text{C}$ .

The following information will be collected after IMP administration:

- Obtain Child-Turcotte-Pugh score and class (A, B, or C).
- AE monitoring.
- Record concomitant medications.

The following will be collected 2 hours after the end of the IMP infusion:

- Collect PK sample

#### **6.1.4 Follow-up (14-28 Days After Final Dose; Weeks 53-55 $\pm$ 3 Days)**

Within 14 to 28 days after the final 26th dose of IMP or, where feasible, following study termination, the following information will be collected ([Table 12-2](#)):

- Enter the IWRS and register subject visit data
- Perform a limited physical examination including weight and examination of the heart, lung, and abdomen)
- Collect vital sign measurements (including heart and respiratory rate, blood pressure, and body temperature)

- Conduct a FibroScan
- Perform MBT (if available)
- Collect biomarkers blood sample (will include the ELF test, FibroTest [FibroSure], and galectin-3)
- Perform EGD (must be performed on a different day within the 14 to 28-day follow-up period than when the HVPG assessment is performed)
- Perform HVPG
- Obtain a liver biopsy
- Perform hematology testing
- Perform blood chemistry testing
- AE monitoring
- Record concomitant medications

### **6.1.5 Follow-up/Early Termination (Week 57 ± 3 Days)**

Fourteen days after the previous visit ([Section 6.1.4](#)), the following information will be collected ([Table 12-2](#)):

- Enter the IWRS and register subject visit data
- Perform a 12-lead ECG assessment
- Perform a limited physical examination (including weight and examination of the heart, lung, and abdomen)
- Collect vital sign measurements (including heart and respiratory rate, blood pressure, and body temperature)
- AE monitoring

- Record concomitant medications

### **6.1.5.1 Open-Label Safety Extension Study**

Following study completion, subjects will be offered enrollment into a subsequent separate study, an OLES if there is adequate tolerability and no safety issues or signs of clinical progression that would recommend discontinuation.

### **6.1.6 End-of-Study Telephone Contact**

Subjects who do not enroll in the OLES will be contacted via telephone every 6 months for 2 years, and annually thereafter for a total of 4 years, for a brief update. Subjects are to be assessed for survival, listing for a liver transplant or the performance of a liver transplant, or complications of chronic liver disease (ascites, spontaneous bacterial peritonitis, variceal bleeding, and encephalopathy; [Table 12-3](#)).

## **6.2 Efficacy Assessments**

Refer to the Study Manual for specific procedures to be followed for the various efficacy assessments. Timing of the efficacy assessments is provided in the schedule of events in [Table 12-2](#), and [Table 12-3](#).

### **6.2.1 HVPG Measurement**

Evaluation of portal hypertension will be done using HVPG measurement. Subjects without varices or with small varices will have hepatic venous catheterization with measurement of both wedged and free hepatic venous pressures and standardized calculation of the HVPG prior to randomization and first IMP dose. All HVPG pressure tracings will be performed according to the study guidelines provided in the Study Manual. All HVPG tracings will be evaluated at a central reading facility by a single experienced investigator ([name], Yale University) to confirm that the subjects meet criteria for inclusion prior to randomization.

Blinded paired HVPG tracings from prior to randomization and at the end of the study will be evaluated at the same central facility by the experienced investigator.

## 6.2.2 Liver Biopsy

Liver biopsies will be evaluated to determine the general pathological diagnosis and to quantitatively evaluate the degree of liver fibrosis. In a central pathology laboratory, paired biopsies from baseline and the end of treatment for each individual will be stained with Sirius red, which stains specifically type I collagen, and digital morphometry used to quantitate the percentage of the liver biopsy that stains with Sirius red, as previously described (McHutchison 2010). The change in liver collagen (a surrogate for fibrosis) will be measured by the change in the CPA at 1 year on paired liver biopsies from prior to randomization and at the end of study. All liver biopsies will be performed according to the study guidelines provided in the Study Manual. Liver biopsies will be evaluated at a central pathology laboratory by a single, experienced pathologist ([name], INNOVA Medical Center).

In addition, as exploratory endpoints, liver biopsies will be stained with antibodies to alpha smooth muscle and galectin-3 and similarly quantified (McHutchison 2010). The change in staining of these 2 proteins will be compared for each subject at baseline and the end of treatment.

## 6.2.3 FibroScan

FibroScan is an FDA approved, noninvasive diagnostic instrument that uses an electromechanical vibrator and pulse-echo ultrasound to evaluate the elastic shear wave in liver tissue which is a measure of liver stiffness. The stiffness of the liver is recorded as the pressure measurement of kPa. The stiffness of the liver correlates with the degree of liver fibrosis as assessed by liver biopsy, including subjects with NASH (Wong 2010). One advantage of this method is that the volume of liver tissue assessed is approximately 100 times greater than volume assessed by liver biopsy. As such, FibroScan represents a promising noninvasive, outpatient method for measuring changes in liver fibrosis over time. FibroScan evaluations will be performed after an 8-hour fast according to the study guidelines provided in the Study Manual and as per the manufacturer's instructions.

## 6.2.4 C-methacetin Breath Test

The MBT is a noninvasive tool to assess microsomal capacity to metabolize the nonradioactive C-labeled methacetin. For those study centers where the MBT is approved,

the test will be performed after an 8-hour fast according to the study guidelines provided in the Study Manual and as per the manufacturer's instructions. The study center will make a follow-up telephone call to the subject to capture any AEs that may have occurred within 48 hours after the breath test.

The Breath Test System consists of the BreathID® MCS device and a test kit containing a breath collection cannula and a nonradioactive isotope C-methacetin solution. The BreathID device measures and computes the CO2/CO2 ratio in the subject's exhaled breath in real time.

The device is based on an FDA-approved device (510k#: K130524) for assessment of *Helicobacter pylori* infection in the stomach utilizing C-urea as a substrate. Performance and safety of the device utilizing the C-methacetin substrate for assessment of liver function have been studied in thousands of subjects worldwide, including in a large US pivotal study (G080107) enrolling over 400 subjects with chronic liver disease from 11 participating sites (including 141 subjects with biopsy proven cirrhosis). This study demonstrated an excellent safety profile of the MBT. Furthermore, there are currently 2 ongoing studies (G140190, G140254) for detection of clinically significant portal hypertension in subjects with advanced liver disease and for assessment of correlation to severity of liver disease in subjects with NAFLD.

The MBT parameter to be used in the current study is the cPDR30, which is the cumulative percentage dose recovery of the metabolized C-methacetin 30 minutes after ingestion of the test substrate. It is obtained by using the following steps:

1. All delta over baseline (DOB) measures with corresponding time point (Tn) will be noted on the eCRF. Each DOB will be plotted by the BreathID device using the following formula:

$$\text{DOB} = {}^{13}\text{CO}_2/{}^{12}\text{CO}_2 @T_n - {}^{13}\text{CO}_2/{}^{12}\text{CO}_2 @T_0$$

where T0 is the baseline sample time (0) and Tn is the time point of the post-ingestion sample in minutes.

2. The DOBs will be transformed into percentage dose recovery rates (PDRs) at a specific time point (n) by using the following formula:

$$\text{PDR}_n = 1.817853 * \text{DOB}_n \times w^{0.5378} \times h^{0.3963}$$

While: w = weight (in kg), h = height (in cm)

3. The following formula will be used to obtain cPDR30:

$$cPDR_{30} = \frac{T_1 \cdot PDR_1}{60} + \sum_{i=2}^n \frac{T_n - T_{n-1}}{60} \cdot \frac{(PDR_n - PDR_{n-1})}{2} + \frac{T_n - T_{n-1}}{60} \cdot PDR_{n-1}$$

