8.2. Key Secondary Efficacy Endpoints

There are six key secondary efficacy endpoints: CPA, Ishak histopathological stage, FibroScan[®], MBT, Brunt-Kleiner histopathological stage and complications of cirrhosis.

CPA

CPA will be used to measure liver collagen (a surrogate for fibrosis) by evaluation of liver biopsy at screening and 14 to 28 days after final dose (53 to 55 weeks). A single experienced pathologist, [name] (INNOVA Medical Center), will evaluate all liver biopsies at a central pathology laboratory.

The CPA will be summarized for the FAS population by visit and treatment group, for all scheduled visits, along with the change from baseline descriptively in a summary table and graphically.

Ishak histopathological stage

Fibrosis will be evaluated by liver biopsy and be staged according to the Ishak histopathological stage (0-6) at screening and 14 to 28 days after final dose (53 to 55 weeks). The number and percentage of subjects by Ishak histopathological stage will be summarized using the FAS population by treatment group. The number and percentage of subjects changing in Ishak histopathological stages will also be presented.

FibroScan[®]

FibroScan[®] will be only performed at the study centers where it is available and used to evaluate liver stiffness which is recorded as the pressure measurement of kPa at the scheduled visits.

The FibroScan[®] (if available) will be summarized for the FAS population by visit and treatment group, for all scheduled visits, along with the change from baseline descriptively in a summary table and graphically.

MBT

The MBT will only be performed at the study centers where it is approved. The cumulative percentage dose recovery of the metabolized ¹³C-methacetin 30 minutes after ingestion of the test substrate will be used as the MBT parameter for this study. Delta over baseline (DOB) with corresponding time point (T_n) will be collected on the eCRF.

The $cPDR_{30}$ is defined as:

$$cPDR_{30} = \frac{\frac{T_1}{60} \cdot PDR_1}{2} + \sum_{i=2}^n \frac{\frac{T_i - T_{i-1}}{60} \cdot (PDR_i + PDR_{i-1})}{2}$$

where $PDR_i = 1.817853 \times DOB_i \times w^{0.5378} \times h^{0.3963}$, $w = weight$ (kg), $h = height$ (cm).

Brunt-Kleiner histopathological stage

Fibrosis will be evaluated by liver biopsy and be staged according to the Brunt-Kleiner histopathological stage (0-4) at screening and 14 to 28 days after final dose (53 to 55 weeks).

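### The breath-test conversion gives DOB no unit, and with the constant 1.817853 neither per-mil nor raw-ratio input yields the percentage of dose that cPDR30 is meant to be

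*Protocol*

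**What the plan says.** Protocol 6.2.4 derives the breath-test endpoint in three steps.

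- **Step 1** covers DOB: "Each DOB will be plotted by the BreathID device using the following formula". The formula is the 13CO2/12CO2 ratio at time Tn minus the ratio at T0. Times are in minutes. No unit, scaling or reference standard is given for DOB.
- **Step 2** converts DOB to PDR: "The DOBs will be transformed into percentage dose recovery rates (PDRs) at a specific time point (n"). The formula uses the constant 1.817853 and the body-size terms w^0.5378 and h^0.3963. The only units given are "While: w = weight (in kg), h = height (in cm").
- **Step 3** sums PDR over the sampling intervals, dividing minutes by 60. PDR is therefore percent of dose per hour. The protocol describes the result, cPDR30, thus: "which is the cumulative percentage dose recovery of the metabolized" methacetin at 30 minutes.

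SAP 8.2 prints the same conversion, beginning "PDR_i = 1.817853", with the same exponents. It has DOB recorded on the eCRF, so the analysis computes cPDR30 from those records. SAP 8.2.1 places the breath test fourth of six gated key secondary endpoints. It is analysed by ANCOVA of change, with the baseline breath-test value as covariate.

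**The concern.** A cumulative percentage of dose must lie between 0 and 100. The multiplier in step 2 exceeds 100 per unit of DOB for adults of ordinary size, so the result depends entirely on the scale on which DOB is entered. That scale is not stated. On the two readings a programmer would try first, per mil and the ratio difference as printed, the output is respectively impossible or close to zero.

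If the SAP formula is programmed as written, the arm means, treatment difference and confidence interval of a key secondary endpoint will be labelled as percentage of dose without being that. They could not be interpreted or compared with any reference value. Comparing protocol with SAP cannot reveal the problem, because both print the same constant.

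**Working it through.** **Inputs from the documents:** constant 1.817853; exponents 0.5378 and 0.3963; weight in kg; height in cm; integration in hours over 30 minutes.

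**Not in the documents:** the DOB unit, methacetin dose, CO2 output, reference isotope ratio, and any expected DOB or cPDR30. There is no worked example to reproduce, and the constant cannot be rebuilt from the plan alone.

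**1. Multiplier and ceiling.** PDR per unit DOB is m = 1.817853 × w^0.5378 × h^0.3963. For a mean DOB of D over 30 minutes, cPDR30 = 0.5 × m × D. It reaches 100% at D = 100/(0.5m) and 1000% at ten times that value. The last column takes DOB as a raw ratio difference and assumes that breath 13C stays doubled throughout (DOB = 0.011), so cPDR30 = 0.5 × m × 0.011.

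| Weight, height | m | D for 100% | D for 1000% | Raw ratio, 13C doubled |
|---|---|---|---|---|
| 60 kg, 155 cm | 121.3 | 1.65 | 16.5 | 0.67% |
| 75 kg, 165 cm | 140.2 | 1.43 | 14.3 | 0.77% |
| 90 kg, 170 cm | 156.5 | 1.28 | 12.8 | 0.86% |
| 110 kg, 175 cm | 176.3 | 1.13 | 11.3 | 0.97% |
| 130 kg, 185 cm | 197.2 | 1.01 | 10.1 | 1.08% |

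**2. DOB in per mil (assumption), using the SAP sum.** Take 90 kg and 170 cm, 5-minute samples, and DOB rising linearly to a plateau at 10 minutes. The time-weighted area is 25/60 hour × plateau, so cPDR30 = (25/60) × 156.5 × plateau:

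- plateau 5: about 326%
- plateau 20: about 1304%
- plateau 40: about 2608%

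The protocol and SAP sums appear to treat the first interval differently, but this does not matter here. In one illustrative profile they gave 1177% and 1170%.

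**3. DOB as a raw ratio difference.** A mean rise of 20 per mil, on an assumed natural ratio of 0.0112, is a ratio difference of 0.000224. Then 0.5 × 156.5 × 0.000224 = 0.018%.

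**4. How far off is the constant on the per-mil reading?** A mass balance gives the constant that would be expected:

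c = 0.001 × R × V × 0.024265 × 100 / dose in mmol

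The assumptions are R = 0.0112372 (reference ratio), V (CO2 output per m²), a body-surface factor of 0.024265 and a molar mass of 166.2.

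- V = 300 mmol/h/m², dose 75 mg: c = 0.01813, and 1.817853/c = 100.3
- V = 350, dose 25 mg: c = 0.06345, ratio 28.7
- V = 200, dose 150 mg: c = 0.00604, ratio 300.9

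Over doses of 25–150 mg and V of 200–350, the printed constant is therefore about 29 to 301 times too large.

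**5. Effect on the test.** Multiplying every breath-test value, baseline included, by k multiplies the treatment coefficient and its standard error by k. The test statistic does not move. In a simulated three-arm ANCOVA with k = 100, the estimates went from 0.544 and 1.865 to 54.4 and 186.5. The p-values stayed at 0.5500 and 0.0418.

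**The case against.** The strongest reply is that this is a missing unit and not a demonstrated error. Section 6.2.4 refers to the Study Manual and the manufacturer's instructions, and DOB comes from the device, so a scale may be fixed there. Some other scale could also give values inside 0 to 100%. With DOB as a relative fraction, a 20 per-mil rise at 90 kg and 170 cm gives 0.5 × 156.5 × 0.02 = 1.6%. A scale error also changes no p-value and no gate.

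The point about inference stands in full. The point about unseen sources means that one cannot say results have been misreported. It does not rescue the formula as printed: the SAP gives programmers an explicit calculation with no unit. Under the same mass balance the fraction reading is too small by about 3 to 35 times (1000/301 to 1000/28.7).

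Three stronger conclusions are tempting, and the documents do not support them:

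- **An exact 100-fold error.** With 300 mmol/h/m² and 0.45 mmol of substrate the balance gives 0.018178, the printed digits shifted by two places. That is suggestive, but those inputs and the per-mil unit are all assumptions, and 50 mg with 200 mmol/h/m² gives the same ratio. On the raw-ratio reading the constant is too small, not too large.
- **Typical values above 1000%.** This needs a mean DOB above about 10 to 16 per mil, and neither document gives a typical DOB.
- **Wrong cut-points in the algorithm of Protocol 7.9.6.** The cut-point there is on a score fitted to these same data. Ordinary logistic regression absorbs a constant rescaling of a predictor into its coefficient, and the analysis is exploratory.

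**Conclusion.** The point holds as a scale error in a printed formula that lacks a unit. With DOB in per mil (assumption), cPDR30 breaches its 100% ceiling at any mean 30-minute DOB above about 1.0 to 1.65 for body weights of 130 down to 60 kg. With DOB as the printed ratio difference, cPDR30 stays at about 1% or less even if breath 13C doubles (natural ratio of about 0.011 assumed). Neither is a usable percentage of dose.

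The size of the error on the per-mil reading is conditional: about 29 to 301 times over the assumed doses and CO2 outputs, and about 100 at one central set. The harm is confined to the reported scale of one gated key secondary endpoint, namely its means, treatment difference and confidence interval. Hypothesis tests and the gatekeeping sequence are unaffected. It should be corrected because the fix is cheap and the formula, followed exactly, does not deliver the quantity that the endpoint names.

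**What to change.** In Protocol 6.2.4 (steps 1 and 2) and SAP 8.2:

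1. State the unit in which DOB is recorded on the eCRF and entered in the formula.
2. Verify the constant against the device manufacturer's conversion before programming and correct it if needed. The value 0.01817853 is only a candidate, valid under the per-mil and mass-balance assumptions above.
3. Add a programmed check that every cPDR30 lies between 0 and 100%. This exposes a scale that is too large but not one that is too small, so it supplements items 1 and 2 and does not replace them.

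The cost is one unit statement and one verified constant in each document, one query to the manufacturer and one line of code. No procedure, visit or data collection changes.
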